- The anesthesia ventilator will be pre-programmed to Pressure Control mode at 15cm H₂O with a rate of 10 breaths/minute and an inspiratory:expiratory ratio of 1:3
- A video recording device will be available to record data from the anesthetic monitor

C. Induction/Airway Management. On arrival to the operating room:

- 1) Apply standard ASA monitors
- 2) Apply Entropy monitor (measures depth of anesthesia via evaluation of brain EEG and quantitative Train of Four (TOF, routine intraoperative monitor which measures level of paralysis via evaluation of the response to electrical stimulus)monitors
- 3) Pre-oxygenate until end tidal O₂ is >90% or for >3 minutes
- 4) Research assistant will open the randomization envelope but not disclose the randomized device order to the clinical team
- 5) IV Induction: 1-2mg midazolam, 50-100mcg fentanyl, 60-100mg lidocaine and 1-2mg/kg propofol.
- 6) Maintenance of anesthesia: 100mcg/kg/min propofol started at time of induction.
- 7) Once lid reflex is lost, obtain a baseline quantitative train-of-four (TOF) and administer rocuronium 1mg/kg of real body weight
- 8) One-handed mask ventilation (MV), without an oral airway, is initiated by the Certified Nurse Anesthetist (CRNA). If one-handed MV without an oral airway is insufficient to return any EtCO₂, a “two-handed jaw-thrust” technique, without an oral airway, is utilized until paralysis/anesthetic depth measures are met. If two-handed technique is insufficient, the 28Fr nasopharyngeal airway is placed and two-handed technique restarted. If two-handed MV with a 28Fr nasopharyngeal airway does not return any EtCO₂, proceed to step #10.
- 9) Once the quantitative TOF is <20% and Entropy reading is 40-60[3], proceed to step 10
 - If, after 90 seconds, the TOF is not <20%, continue to MV until the TOF is <20%
 - If, after 90 seconds, the Entropy reading is not 40-60, increase propofol by 50mcg/kg/min every minute and continue MV until reading is 40-60
- 10) The CRNA (who is performing MV) is asked to turn away so as to be blinded to oral airway placement order
- 11) The RN research assistant or study medical student (both formally trained, with documentation, in oral airway placement) will place the device randomized to be first using the below methods and then cover the patients nose and mouth with the opacified anesthesia mask
 - Guedel oral airway: Insert with concavity facing upward then turn 180 degrees as advancing the proximal bevel to the level of the teeth

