- AOA: In the “closed” conformation, insert with concavity facing upward then turn 180 degrees as advancing the proximal bevel to the level of the teeth. Once at the level of the teeth, bring proximal ends together to lock in the fully ‘open’ conformation

12) The CRNA will turn back to the patient and secure the anesthesia mask utilizing “2-handed jaw-thrust” technique.

13) The ventilator is turned on and the following data is recorded, via video of the anesthetic monitor, for breaths # 6-10:

-Inspiratory tidal volumes

-Expiratory tidal volumes

-EtCO₂ waveform

Note (a): If EtCO₂ is not achieved after 5 breaths with first device, proceed immediately to step #14

Note (b): No video or images will be taken of the patient or patient identifiers, just the anesthesia monitor and the device randomized to be placed first

14) The CRNA will then turn away from the patient and the RN research assistant or study medical student will remove the oral airway, noting the presence of any blood on the device (first device only)

15) Steps 10-13 will be repeated for the device randomized to be placed second, then the anesthetic will proceed at the discretion of the providers

Note: If EtCO₂ is not achieved after 5 breaths with the second device, the protocol is ended and the ASA Difficult Airway Algorithm is followed

D. Post-operative:

15-45 minutes after "Anesthesia Stop" time, the research assistant or study medical student will:

- Perform an oropharyngeal exam for signs of trauma

- Ask the patient to grade their degree of “sore throat” (subjectively, from 0-10)

E. Data Review:

-The video taken during step 13 above will be uploaded to a password-protected server to which only study personnel will have access. The video will contain no images of the patient or patient identifiers, just the anesthesia monitor and the device randomized to be placed first

-The blinded primary investigator ([name]) will transcribe clinical data (expiratory and inspiratory tidal volumes and EtCO₂ waveforms) from the above video

VII.E.7

Will you attempt to recontact subjects who are lost to follow-up?

No - followup is not required in this study

VII.E.9

Will subjects be provided any compensation for participating in this study?

No

VIII. Risks

VIII.1

What are the risks to subjects including

- emotional or psychological

- financial

- legal or social

- physical?

- Emotional or psychological: None foreseen

- Financial: None foreseen

- Legal or social: None foreseen

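### Step 9 answers any Entropy reading outside 40-60 with more propofol, which is the wrong action for a patient already deeper than the band

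*Combined protocol and SAP*

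**What the plan says.** All of the dosing text is in the combined protocol and SAP, section VII.E.6, part C (Induction/Airway Management).

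- Step 2 attaches the monitor and says what it is for: "Apply Entropy monitor (measures depth of anesthesia via evaluation of brain EEG". The document does not say which end of the scale means deeper.
- Step 5 gives the induction drugs: midazolam, fentanyl, lidocaine and a propofol bolus of 1-2 mg/kg.
- Step 6 sets the starting infusion: "100mcg/kg/min propofol started at time of induction".
- Step 8 describes mask ventilation without an oral airway. The two-handed technique, if needed, "is utilized until paralysis/anesthetic depth measures are met".
- Step 9 sets the condition for moving on to device placement: "Once the quantitative TOF is <20% and Entropy reading is 40-60[3], proceed to step 10".
- Step 9 then gives one instruction for each measure that has not met its target. For paralysis: "If, after 90 seconds, the TOF is not <20%, continue to MV until the TOF is <20"%. For depth: "If, after 90 seconds, the Entropy reading is not 40-60, increase propofol by 50mcg/kg/min every minute and continue MV until reading is 40-60".

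The supplied text has no instruction to hold or reduce propofol, and it sets no separate action for each side of the Entropy band.

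**The concern.** The condition for proceeding has a lower and an upper limit, but the corrective action has only one direction. A reading that misses the band may mean the patient is too light or too deep, and the text sends both to the same repeated increase in propofol. The train-of-four instruction beside it does not have this difficulty: its criterion is one-sided and its action is only to keep ventilating.

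What is at stake is patient safety and adherence to the protocol. Faced with an over-deep patient, staff must either give anesthetic that the plan's own target says is not needed, or depart from the written procedure. A study-directed dosing instruction should not depend on being disregarded.

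**Working it through.** **Logic of the rule.** The only premise not written out in the document is that more propofol deepens anesthesia, which step 9 itself presupposes.

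| State at the check | Written action | Direction relative to 40-60 |
|---|---|---|
| In the band, train-of-four below 20% | Go to step 10 | Target met |
| Lighter than the band | Raise propofol each minute | Toward the band |
| Deeper than the band | Raise propofol each minute | Away from the band |

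The third row holds whichever end of the Entropy scale means deeper, because one side of a two-sided band must be the deeper side.

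**Is there another instruction for the third row?** The other provisions that could release such a patient are these:

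- Step 8 goes straight to step 10, but only for failed ventilation: "If two-handed MV with a 28Fr nasopharyngeal airway does not return any" end-tidal CO₂.
- Section VIII.2 abandons the study for difficulty in managing the airway. Excess depth is not a trigger.
- Step 15 mentions discretion over the anesthetic after the second device: "then the anesthetic will proceed at the discretion of the providers".
- Section VIII.4 provides a review of combined data, which is not a rule for one patient.

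None of these tells staff what to do with propofol when the reading is too deep. The written way on is a reading of 40-60, however it comes about. It may still come about as the bolus wears off, but the instructed action works against it.

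**Dose the text permits.** The plan gives no figure here to reproduce. Inputs: starting rate 100 mcg/kg/min (step 6); increment 50 mcg/kg/min every minute, starting after 90 seconds (step 9). Assumptions: the first increase comes at exactly 90 seconds and each rate is held for one minute.

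- Time of the *n*th increase = 1.5 + (*n* − 1) minutes.
- Rate after *n* increases = 100 + 50*n* mcg/kg/min.
- Propofol above the starting infusion, to the end of the *n*th minute of increases = 50 × (1 + 2 + … + *n*) = 25*n*(*n* + 1) mcg/kg.

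| *n* | Time of increase | Rate (mcg/kg/min) | Multiple of start | Extra propofol |
|---|---|---|---|---|
| 1 | 1.5 min | 100 + 50 = 150 | 1.5 | 25 × 1 × 2 = 50 mcg/kg by 2.5 min |
| 2 | 2.5 min | 100 + 100 = 200 | 2.0 | 25 × 2 × 3 = 150 mcg/kg (0.15 mg/kg) by 3.5 min |
| 4 | 4.5 min | 100 + 200 = 300 | 3.0 | 25 × 4 × 5 = 500 mcg/kg (0.50 mg/kg) by 5.5 min |

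Against the 1-2 mg/kg induction bolus, 0.15 mg/kg is 0.15/2 = 7.5% to 0.15/1 = 15%, and 0.50 mg/kg is 25% to 50%. If propofol were increased only on the lighter side, the extra for an over-deep patient would be 0.

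This shows what the wording allows. It is not an estimate of risk, because the document does not say how often a patient is deeper than the band at 90 seconds.

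**The case against.** The strongest reply is that the meaning is plain from context. Step 8 ventilates until the depth and paralysis targets are met, and step 9 continues with what to do if they have not been met after 90 seconds. Read that way, the instruction is for patients who are not yet ready, and for them more propofol is sensible. A nurse anesthetist is ventilating the patient with the depth monitor attached, a staff anesthesiologist takes part in the study, and section VII.D.29 promises the same standard of care to those who enroll. Literal escalation in a patient who reads too deep is therefore unlikely. This stands, and it is why the point carries minor weight. It does not correct the sentence, which still prescribes an increase for any reading outside the band.

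The attachment list also names a full study protocol and role sheets for the attending anesthesiologist and the nurse anesthetist, none of which was supplied. They may state which side triggers escalation, or a maximum rate. Section VII.B.11 answers that there is no separate written protocol, so their content is uncertain. The point is therefore about the wording of this form, not about the instructions that clinicians actually received.

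A reader might infer more than the documents support:

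- **That an over-deep patient cannot leave step 9.** The exit is a reading of 40-60 by any route, and the check comes soon after a propofol bolus whose effect may fade. The rule opposes that return; it does not exclude it.
- **That clinicians have no discretion before step 15.** That sentence marks the end of study procedures and does not withdraw clinical judgment before then.
- **That the tidal-volume comparison is biased.** The condition is applied before the first device, and every patient receives both devices in random order.

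**Conclusion.** Wrong as written, with minor weight: a patient-safety dosing rule that gives the correct action on one side of its target band and the wrong action on the other. The conclusion rests on the wording of step 9 and on the premise that propofol deepens anesthesia. It does not depend on the direction of the Entropy scale.

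Under the timing assumptions above, literal compliance doubles the infusion after two increases and triples it after four. The four-step case would need repeated escalation against a monitor showing excess depth, which is improbable. No number of affected patients should be given, since the documents offer no basis for one. The sample size, the margin, the endpoint and the paired analysis are unaffected.

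**What to change.** Reword the depth instruction in step 9 so that:

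1. propofol is increased by 50 mcg/kg/min each minute only when the reading shows anesthesia lighter than the 40-60 band, with that side given as a number (above 60 or below 40, according to the monitor's scale);
2. when the reading shows anesthesia deeper than the band, propofol is not increased, and is held or reduced at the anesthesiologist's discretion while mask ventilation continues.

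The clinical investigators may also wish to state a maximum rate or time, if the attached protocol or role sheets do not already do so. Those attachments should be checked so that they agree with the new wording.

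The cost is one line of text. No procedure, visit, measurement or patient is added.

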I.5 *Specify your research question(s), study aims or hypotheses (do not indicate "see protocol")*

- 1) Does the AOA facilitate mask ventilation (as measured by inspiratory and expiratory tidal volumes and end-tidal CO₂ waveforms) as well as a Guedel oral airway in patients with risk factors for difficult mask ventilation
- 2) Is the AOA non-traumatic as anticipated to the human airway

I.6 *Background and significance and/or Preliminary studies related to this project. (do not indicate "see protocol")*

Brief explanation: The Articulated Oral Airway (AOA) is a novel device in the field of Airway Management which actively facilitates both mask ventilation (breathing for an anesthetized patient without a breathing tube) and fiberoptic intubation (placement of a breathing tube using a flexible

camera). No device currently on the market has this dual functionality. In conjunction with the University of Iowa Research Foundation (UIRF Case# 2014-018) the AOA received US Patent 8,794,230 B2 in August of 2014.

Detailed explanation: A primary goal of all anesthetics is the establishment of a patent airway. The most commonly performed airway management technique is mask ventilation; using a mask over a patient's nose and mouth to breath for them. This technique is made significantly more difficult by certain anatomical features, the most common of which is a large tongue related to obesity. The AOA not only creates a conduit for delivering oxygen and anesthetic agents, but also actively displaces the tongue to optimize the space available for ventilation.

In addition, the AOA can act as a conduit for flexible fiberoptic intubation – a technique of utilizing a flexible guide to navigate airway anatomy and allow placement of a breathing tube ("endotracheal tube," or ETT) with minimal manipulation of a patient's neck and airway. A significant disadvantage of fiberoptic technique is that, for an image to be seen, an "airspace" (a space void of visual obstruction) must be created. If the tip of the fiberoptic scope is touching the patient's airway or any foreign objects in the patient's airway, the result would be analogous to leaving the lens cap on a camera and the necessary anatomy would not be seen.

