VI.2 *What is the age of the youngest adult subject?*
18.0

VI.3 *What is the age of the oldest adult subject?*
99.0

VI.4 *What is the percentage of adult male subjects?*
70

VI.5 *What is the percentage of adult female subjects?*
30

VI.6 *How many minor subjects do you expect to consent or enroll for this project?*
0

VI.13 *Describe EACH of your subject populations*

- *Include description of any control group(s)*
- *Specify the Inclusion/Exclusion criteria for EACH group*

Control group(s): None, each patient will be their own control

Inclusion Criteria: Patients undergoing non-emergent surgery who have two or more of the following risk factors for difficult mask ventilation:

- i. Age > 55 years
- ii. BMI > 30kg/m²
- iii. Beard
- iv. Lack of teeth
- v. History of snoring

Exclusion Criteria:

- a. Documented history of impossible MV
- b. Planned omission of mask ventilation [i.e. Rapid Sequence Intubation ("RSI," a modified induction routine which omits mask ventilation and is used when risk of aspiration is high)]
- c. Planned omission of long-acting paralytics
- d. Need for awake airway management
- e. Need for emergent airway protection
- f. Presence of oropharyngeal anatomic abnormalities
- g. Distance from the maxillary incisors to the angle of the mandible <11cm
- h. <18 years of age
- i. Known pregnant state
- j. Current incarceration
- k. Refusal to be involved in the study

With the above inclusion (i.e. presence of beard) and exclusion (maxillary incisor to angle of mandible distance <11cm) criteria, we anticipate that roughly 70% of eligible patients to be male, as women are less likely to have a beard or high maxillary incisor to angle of mandible distance.

VI.14 *Provide an estimate of the total number of subjects that would be eligible for inclusion in each of your study populations (include your control population if applicable)*
Review of EPIC UIHC Main Operating Room (MOR) and Ambulatory Surgery Center (ASC) schedules show that a typical day consists of 90-110 surgeries. Of these patients, roughly 4-8 patients would be expected to meet inclusion (and not meet exclusion) criteria per day.

VI.15 *Describe how you will have access to each of your study populations in sufficient number to meet your recruitment goals.*
 As per above, there are historically 4-8 patients per day who would qualify for the study. With the goal of consenting 1-2 per day, we should be able to enroll 58 patients in 50-60 OR days, or 10-12 weeks.

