VII.D.10	
Will a member of the research team discuss the study with the subject by phone prior to the subject agreeing to participate?
 
No
				
VII.D.12	
Who will be involved in the consent process (including review of consent document, answering subjects' questions)?
 
  
 Name	Consent Process Involvement	
   
 [name]	Yes	
  
	Name	Consent Process Involvement	[name]	Yes
Name	Consent Process Involvement				
[name]	Yes				
VII.D.15	
Check all materials that will be used to obtain/document informed consent:
 
 • Consent Document 				
VII.D.16	
Are you requesting a waiver of documentation of consent (either no subject signature or no written document)?
 
No
				
VII.D.19	
Before the subject gives consent to participate are there any screening questions that you need to directly ask the potential subject to determine eligibility for the study?
 
Yes
				
VII.D.20	
List any screening questions you will directly ask the potential subject to determine eligibility.
 
Do you have any teeth? Have you ever been told that you have been difficult to intubate? Do you have any airway anatomic abnormalities? Do you snore? Do you have sleep apnea?
				
VII.D.21	
Will you keep a screening log or other record that would include information on people who do not enroll in the study?
 
Yes
				

VII.D.22 *Describe the information being collected and the purpose for keeping this information.*
 We will keep the name of the patient, MRN, date of surgery, reason exclusion or declined & initials of RA that screened patient.

VII.D.23 *Will this information be shared with anyone outside the UI research team members?*
 No

VII.D.25 *After the subject agrees to participate (signs consent), are there any screening procedures, tests, or studies that need to be done to determine if the subject is eligible to continue participating?*
 No

VII.D.27 *Discuss how much time a potential subject will have to agree to consider participation and whether or not they will be able to discuss the study with family/friends before deciding on participation.*

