VII.E.2 *Describe randomization scheme/assignment including ratio such as 1:1, 2:1 etc.*
This study involves a random allocation, cross-over design. All patients will receive both devices - the randomization will determine which of the devices they receive first. There are two reasons for the randomization: 1) As we are evaluating for blood on the airway upon its removal, the order of placement is important as we can only evaluate the first-placed device (we won't know if blood on the second-placed device is from that device or left over from the first device. 2) Without randomization, the CRNA would not be blinded as they would know which device they are using first and second which could introduce bias.

VII.E.3 *Will any questionnaires, surveys, or written assessments be used to obtain data directly from subjects in this study?*
No

VII.E.5 *Does this project involve creating any audiotapes, videotapes, or photographs?*
Yes

VII.E.6 *Provide a detailed description in sequential order of the study procedures following the consent process - DO NOT cut and paste from the Consent Document.*

Describe study populations separately if they will be participating in different procedures - include CONTROL population if applicable.

DESCRIBE:

- *What subjects will be asked to do/what happens in the study (in sequential order)*
- *The time period over which procedures will occur*
- *The time commitment for the subject for individual visits/procedures*
- *Long-term followup and how it occurs*

A. Staff anesthesiologist will perform an airway exam and note the following

- - Age
 - BMI
 - Presence or absence of beard

- Patient dentition
- History of snoring
- Any formal diagnosis of sleep apnea and CPAP/BiPap use and settings
- Mallampati grade (I-IV)
- Mouth opening (in cm)
- Neck extension (full, limited or none)
- Retrognathia (none, mild, significant)
- Any apparent nasal or oral anatomic abnormalities

B. Operating room preparation (performed by research assistant or study medical student):

- A tongue depressor, AOA, and 100mm Guedel oral airway will be available, but out of sight of the clinical providers
- A 28Fr nasopharyngeal airway and water-soluble lubricant will be set on the anesthesia machine next to the laryngoscopy equipment
- The anesthesia circuit facemask will be opacified by internal application of lip balm (as per pediatric routine)
- A pump for delivery of propofol infusion will be available

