- Physical: Potential for risks associated with routine airway management with an oral airway (difficult or failed airway management/oropharyngeal trauma). Potential for risks associated with placement of two oral airways instead of just one or none.

VIII.2

What have you done to minimize the risks?

- *If applicable to this study ALSO include:*
 - *How you (members of your research team at Iowa) will monitor the safety of individual subjects.*
 - *Include a description of the availability of medical or psychological resources that subjects might require as a consequence of participating in this research and how referral will occur if necessary (e.g. availability of emergency medical care, psychological counseling, etc.)*

Pre-procedure: The Articulated Oral Airway is made of bio-compatible material in a ISO 9001:2008 Certified molding facility. The AOA has been tested in manakin models, including pressure testing by members of the UIowa Biomedical Engineering program.

Intraoperative: Per protocol, if difficulty in airway management is encountered, the study is abandoned and emergency airway management protocols (ASA Difficult Airway Algorithm) followed.

Post-operative: An interim safety review will be performed after 20 patients have been enrolled. If there is any significant increase in either trauma or difficult in mask ventilation noted, the study will be stopped.

VIII.3 *Does this study have a plan to have an individual or committee review combined data from all subjects on a periodic basis (such as summary or aggregate safety and/or efficacy data)?*

Yes

VIII.4 *Describe the plan to review combined data from all subjects, such as summary or aggregate safety and/or efficacy data. Include the following:*

- *Describe what data will be summarized and reviewed*
- *Describe how frequently data will be reviewed.*

After the first 20 patients (and any time earlier if concerns are raised by the research team/clinical staff caring for the patients), a unbiased faculty anesthesiologist ([name], as per below) will review intraoperative tidal volumes (marker for adequate ventilation), incidence of blood on first-placed device, and post-anesthesia care unit (PACU) data on post-operative pharyngeal trauma.

VIII.5 *Will overall safety monitoring be performed by individual(s)/committee at The University of Iowa. (NOTE: If this study involves more than minimal risk, in most cases these should be individuals who are not members of the study research team.)?*

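### The recovery-room trauma exam and sore-throat score have no matching pre-induction record, so new findings cannot be told from existing ones

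*Combined protocol and SAP*

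**What the plan says.** Section I.5 sets the second aim: "Is the AOA non-traumatic as anticipated to the human airway". Two kinds of data bear on it.

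- **At removal (VII.E.6, part C, step 14):** any blood on the device, noted for the first-placed device only. VII.E.2 gives this as one of the two reasons for randomising the order.
- **In recovery (VII.E.6, part D), 15-45 minutes after the end of anesthesia:** a research assistant or study medical student is to "Perform an oropharyngeal exam for signs of trauma" and to "Ask the patient to grade their degree of" sore throat from 0 to 10.

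Before induction, part A states: "Staff anesthesiologist will perform an airway exam and note the following". The list covers age, BMI, beard, dentition, snoring, sleep apnea and its treatment, Mallampati grade, mouth opening, neck extension and retrognathia. It ends with "Any apparent nasal or oral anatomic abnormalities".

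The exclusion criteria in VI.13 include "Presence of oropharyngeal anatomic abnormalities", and the screening questions in VII.D.20 include "Do you have any airway anatomic abnormalities".

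For safety, VIII.2 provides a review after 20 patients and says: "If there is any significant increase in either trauma or difficult in mask ventilation noted, the study will be stopped". VIII.4 names the data for that review: tidal volumes, blood on the first-placed device, and recovery-room data on pharyngeal trauma. Section XI describes no analysis of trauma or sore throat.

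**The concern.** The first listed look for injury, and the only sore-throat score, come after both devices have been used and the operation is over. The part A list and the screening questions deal with anatomy, teeth and history. An abrasion, an ulcer, a bleeding gum, a chipped tooth or a sore throat on the morning of surgery has no listed place to be written down. No rule tells the recovery-room examiner to discount what was already there, and that examiner is not the anesthesiologist who did the pre-induction exam.

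Section VI.13 says each patient serves as their own control. That works for tidal volume, which is measured with each device. It does not work for the recovery-room outcomes, which are measured once, after both devices, with no earlier value from the same patient.

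Two results are at stake: the absolute rates of recovery-room trauma and sore throat, and the pharyngeal-trauma data seen at the 20-patient review. The error can run either way. An old lesion may be read as device injury, or a real injury may be explained away as old because no record says otherwise.

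**Working it through.** **Step 1. What is recorded before and after.**

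| Item | Before induction (VII.E.6 A; VII.D.20) | In recovery (VII.E.6 D) |
|---|---|---|
| Gross oral anatomy | Yes; abnormalities are also an exclusion | Not itemised |
| Dentition | Yes, but not as injury | Not itemised |
| Mucosal or dental injury, bleeding | Not listed | Within the exam for signs of trauma |
| Sore throat, 0-10 | Not listed | Yes, once |

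The two items that form the recovery-room outcomes are the two with no earlier entry.

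**Step 2. Which results are exposed.**

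- Recovery-room trauma and sore throat, as absolute results: exposed.
- Pharyngeal trauma at the 20-patient review: exposed, since VIII.4 names it.
- Sore throat at that review: VIII.4 does not name it.
- Blood on the first-placed device: existing lesions fall on average equally on the AOA-first and Guedel-first groups, so the comparison does not lean toward either device.

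**Step 3. Possible size.** The documents give no rate of existing findings, so the rate p is an assumption, taken from 2% to 15%. If every existing finding were counted as trauma, the expected number is n × p and the chance of at least one among 20 is 1 − (1 − p)^20.

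| p (assumed) | Expected of 20 | Chance of at least one of 20 | Expected of 58 |
|---|---|---|---|
| 2% | 20 × 0.02 = 0.4 | 1 − 0.98^20 = 33% | 58 × 0.02 = 1.2 |
| 5% | 20 × 0.05 = 1.0 | 1 − 0.95^20 = 64% | 58 × 0.05 = 2.9 |
| 10% | 20 × 0.10 = 2.0 | 1 − 0.90^20 = 88% | 58 × 0.10 = 5.8 |
| 15% | 20 × 0.15 = 3.0 | 1 − 0.85^20 = 96% | 58 × 0.15 = 8.7 |

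The expected counts are ceilings for each p. The exam looks for signs of trauma, not for any lesion, and no sore-throat cut-off defines trauma.

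**Step 4. The plan's own figures.** The plan states no number for trauma or sore throat. Its sample size (XI.2) belongs to the tidal-volume test: margin 1 ml/kg, SD of the paired difference 2.5 ml/kg, one-sided 0.05, true difference 0. An exact paired t calculation gives power 0.9005 at n = 55, which matches the stated 90%. The 3 allowed failures bring recruitment to 55 + 3 = 58. Nothing in this point changes those figures.

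**The case against.** The other side has a good deal to say, and most of it limits how far the point reaches.

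- **There is a pre-operative exam.** A reader might infer that no baseline exists at all. That is too broad: dentition and apparent oral anatomic abnormalities are recorded, and oropharyngeal abnormalities are an exclusion. This stands for anatomy. It does not cover mucosal injury, bleeding or soreness.
- **The safety stop.** A reader might infer that a sore throat on arrival could help stop the trial. The documents do not say so: neither VIII.4 nor Aim 2 names the sore-throat score. Nor need the increase in VIII.2 mean a change within a patient. The same phrase covers difficult mask ventilation, and it could mean more than expected or more than with the Guedel airway. The missing reference rate is a separate matter.
- **The device comparison.** A reader might infer that Aim 2's comparison is biased. Blood on the first-placed device is the one device-specific measure, and randomised order protects it on average.
- **The population.** A reader might suppose that these patients are prone to oral lesions. Entry needs any two of five factors, and age with BMI is enough. The documents give no basis for a high rate.
- **Attribution.** Even a clearly new lesion cannot be assigned to the AOA. Every patient has both devices, some also a nasopharyngeal airway, and further airway management follows at the providers' discretion. This stands in full, and a baseline does not cure it.
- **Unseen forms.** The data collection forms and a fuller protocol are listed as attachments but not shown, so a baseline item there cannot be ruled out. The part A list is nonetheless itemised and lacks one.

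**Conclusion.** The point holds within limits. As the procedures are listed, the recovery-room exam and sore-throat score cannot separate new from existing findings. The absolute recovery-room results, and the pharyngeal-trauma data reviewed after 20 patients, can therefore be inflated. The size is unknown. On an assumed 2-15% of patients with an existing finding, and with every one counted, the ceiling is about 0.4-3 of 20 and 1-9 of 58.

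The primary outcome, sample size and power are untouched. The change is still worth making: without it, existing findings cannot be removed from these data afterwards, and the remedy is very cheap.

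**What to change.** 1. Add two fields to the part A exam: the same 0-10 sore-throat score, and a yes/no record, with site, of existing oral mucosal or dental injury or bleeding.
2. Report the recovery-room outcomes as new or worsened lesions and as change in sore-throat score.
3. Give the anesthesiologist who does the VIII.4 review new or worsened pharyngeal trauma.
4. State that these outcomes reflect the whole airway-management sequence (both devices, any nasopharyngeal airway, later airway management) and cannot be attributed to the AOA alone. The device comparison for Aim 2 then rests on blood on the first-placed device.
5. If the attached forms already hold such items, add them to the part A list so that the two agree.

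The cost is under a minute per patient and two fields on an exam already done in everyone. No extra visit or staff is needed, and sample size, power and significance level do not change.
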